Esophageal self-dilation therapy (ESDT), where the patient learns to pass a polyvinyl dilator orally on a routine basis, has been in practice since at least the 1970s, however, no prospective studies have evaluated the outcomes ESDT. The largest study to date on ESDT retrospectively studied 30 patients¹², and all the published studies on this topic consists of less than 50 patients in total¹²⁻¹⁹. In these retrospective and observational studies, ESDT appears to be effective for RBES, reducing the number of endoscopic dilations from an average of 21.7 to an average of 1¹². However, many questions with regards to ESDT remain unanswered. Firstly, in the absence of any prospective data it is uncertain how effective ESDT is. Moreover, currently patients are offered ESDT when standard therapies fail.

Hypotheses:

Among patients with refractory benign esophageal stricture who were treated endoscopically, we hypothesized the following:

- 1. Compared to an endoscopy as needed approach, esophageal self-dilation therapy decreases the number of endoscopic dilations and prolongs dysphagia free intervals
- 2. Esophageal self-dilation therapy is a safe and well tolerated therapy
- 3. ESDT significantly lowers health cost in managing refractory esophageal stricture

Primary Aims:

1. Assess the clinical efficacy of ESDT for patients with RBES defined as number of endoscopic interventions 6 months following serial dilation

Secondary Aims:

- 1. Length of intervention free interval and dysphagia score
- 2. Evaluate factors which could influence clinical success of ESDT including etiology and location of the stricture
- 3. Assess the safety of ESDT by identifying clinically significant adverse events including perforation, bleeding and pain.
- 4. Assess acceptance of ESDT by measuring the number of patients who accepts the procedure and are able to complete it over the total number of patients offered ESDT
- 5. The cost saving in ESDT compared to the current standard of care (repetitive endoscopic dilation)
- 6. Evaluate long term outcomes of self-dilatation at 3, 6, 9 and 12 months following participation in the 6 month randomized or prospective observational trial

Methods:

Study Design:

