- 2. Patients in the randomized observation group will receive endoscopic dilation as needed with charges to the patients and their health insurance as appropriate since this is the standard of care
- 3. Patients in both groups will receive stipend of \$25 for each questionnaire for the time spent in completing the dysphagia questionnaire during the randomized 6 month study duration
- 4. Patients who participate in the prospective observational study, and who either chose self-dilation or observation will receive stipend of \$25 for each questionnaire for the time spent in completing the dysphagia questionnaire

Patients who agree to the prospective extension study will receive a stipend of \$25 for each of the 4 monthly MDQ phone calls to collect questionnaires.

Statistical Analysis:

Sample Size Estimation:

Based on the current knowledge from our prior experience, the clinical success of ESDT appears to be 80%. The clinical success of repetitive endoscopic dilation is reported in the literature to be 30%. Assuming a 50% improvement in clinical success with ESDT and using 1:1 randomizing, the estimated minimum number of patients needed is 30 patients (15 in each group). Given the extreme paucity of data on self dilation and ambiguity about the potential improvement we intend to recruit 40 patients across the two sites (Rochester and Phoenix). This estimated number will provide at least 80% power of finding a significant difference at a P value of 0.05

Up to 40 patients who chose not to participate in the randomized trial, but who agree to be followed in the prospective observational group will be recruited.

The following table summarizes the key questions and corresponding approaches to be addressed by this study.

Primary Endpoint:

1. Compare the number of endoscopies required in a 6 month interval in patients who achieved at least a 10-12 mm esophageal diameter during serial dilation for RBES and were subsequently treated with ESDT versus standard clinical care.

Secondary Endpoints:

- 1. Determine the length of intervention free interval
- 2. Dysphagia score
- 3. Number of clinically significant adverse events including perforation, bleeding and pain
- 4. Cost of ESDT compared to the current standard of care (repetitive endoscopic dilation)

Definition:

Perforation will be defined as Evidence of air or luminal contents outside the GI tract. Bleeding will be defined as hematemesis and/or melena or hemoglobin drop >2 g/L

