Question	Approach	Statistical Test
Clinical success	Compare the number of	Logistic regression in a
	patients who remained free	univariate and multivariate
	of endoscopic therapy	analysis
	between the two groups	
Time to the next endoscopy	Compare time endoscopic	Cox regression and Kaplan
	therapy. Patients who	Meier
	requires endoscopic dilation	
	will be considered failure	
Adverse events	Compare the number of	Logistic regression in a
	patients who developed	univariate and multivariate
	adverse events between the	analysis
	two groups	
The cost	Compare the cost of	Linear regression
	treatment including	
	endoscopic therapy,	
	hospitalization from	
	complications	
Factors affecting clinical	Investigating factors which	Multivariate logistic regression
success in ESDT	could determine clinical	
	success including age,	
	gender, etiology, length of	
	the stricture and location of	
	the stricture	

References:

- 1. Spechler SJ. American gastroenterological association medical position statement on treatment of patients with dysphagia caused by benign disorders of the distal esophagus. Gastroenterology 1999;117:229-33.
- 3. de Wijkerslooth LR, Vleggaar FP, Siersema PD. Endoscopic management of difficult or recurrent esophageal strictures. Am J Gastroenterol 2011;106:2080-91; quiz 2092.
- 6. Ramage JI, Jr., Rumalla A, Baron TH, et al. A prospective, randomized, double-blind, placebo-controlled trial of endoscopic steroid injection therapy for recalcitrant esophageal peptic strictures. Am J Gastroenterol 2005;100:2419-25.

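### The safety hypothesis has only a between-group logistic regression behind it, which for uncommon harms at about 20 patients per arm says little; the plan gives no acceptable rate, margin or confidence bound

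*Combined protocol and SAP*

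**What the plan says.** Under Hypotheses, item 2 is a positive claim: "Esophageal self-dilation therapy is a safe and well tolerated therapy". Secondary Aim 3 is softer: "Assess the safety of ESDT by identifying clinically significant adverse events including perforation, bleeding and pain". Secondary Endpoint 3 is a count: "Number of clinically significant adverse events including perforation, bleeding and pain".

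The only analysis tied to these is the Adverse events row of the table at the end of Statistical Analysis. It compares the number of patients with "adverse events between the" two groups, and its Statistical Test column begins "Logistic regression in a" and goes on to univariate and multivariate analysis.

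Sample Size Estimation rests on clinical success of 80% with ESDT against 30% with repeated endoscopic dilation. It arrives at 15 per group and raises the total to 40. Its closing sentence reads: "This estimated number will provide at least 80% power of finding a significant difference at a P value of 0.05". No expected or acceptable adverse event rate, margin, confidence bound or power for harms appears anywhere in the document. Perforation and bleeding are defined; pain is not.

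**The concern.** A test whose null is no difference can show that ESDT is more harmful, or less harmful, than standard care. It cannot show that ESDT is safe. Apart from significantly fewer events on ESDT, the only result compatible with hypothesis 2 is a failure to reject. With about 20 patients per arm and uncommon harms, that is the likely result whether or not ESDT carries a material excess.

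Perforation is where this matters most. An ESDT arm with no perforations would be reassuring to look at, yet the plan provides no figure that tells the reader how large a risk is still compatible with it. The planned method also fails in exactly that case: with zero events in one arm, ordinary logistic regression has no finite odds ratio to report.

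**Working it through.** **Inputs from the document.** 40 randomised patients at 1:1, so about 20 per arm; significance level 0.05, given in the sample size paragraph, with sidedness not stated (two-sided assumed). **Inputs assumed.** All adverse event risks, because the document gives none. No crossover and no dropout.

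**1. The plan's own figure.** For 80% vs 30%, two-sided 0.05 and 80% power, with pooled variance under the null (mean success 0.55):

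n = [1.96 × √(2 × 0.55 × 0.45) + 0.842 × √(0.8 × 0.2 + 0.3 × 0.7)]² / 0.5² = 14.3, so 15 per group.

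The stated 15 per group reproduces; by the same approximation, power is 82% at 15 per arm and 92% at 20. This is power for clinical success and says nothing about harms.

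**2. Chance of missing a true excess on ESDT.** For each of the 21 × 21 possible tables with 20 patients per arm, compute the p-value. Then

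miss = 1 − Σ Bin(a; 20, p_ESDT) × Bin(b; 20, p_control),

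summing over tables with a > b and p < 0.05. The likelihood-ratio and Wald tests are the two usual outputs of a logistic regression; a Wald test with a zero cell is counted as non-significant. Fisher's exact test is shown for reference.

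| Assumed ESDT vs control risk | Likelihood-ratio | Fisher | Wald |
|---|---|---|---|
| 5% vs 1% | 94% | 99.8% | 100% |
| 10% vs 2% | 78% | 97% | 99.9% |
| 20% vs 5% | 63% | 83% | 96% |
| 30% vs 10% | 63% | 76% | 81% |
| 30% vs 5% | 38% | 55% | 80% |
| 60% vs 20% | 25% | 35% | 28% |

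As an example of a single result, 6 of 20 on ESDT against 1 of 20 on standard care gives p = 0.091 (Fisher), 0.065 (Wald) and 0.030 (likelihood-ratio), so the answer depends on which p-value is reported. The plan does not say which.

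**3. How often the regression breaks down.** The chance of no events among 20 controls is (1 − p)²⁰: 0.99²⁰ = 82%, 0.98²⁰ = 67%, 0.95²⁰ = 36%. In each of these cases the odds ratio is infinite or, if neither arm has an event, undefined.

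**4. What zero events would show.** The exact upper bound with 0 of n events is 1 − α^(1/n).

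- 0 of 20, one-sided 95%: 1 − 0.05^(1/20) = 13.9%.
- 0 of 20, two-sided 95%: 1 − 0.025^(1/20) = 16.8%.
- 0 of 20 in both arms, Newcombe 95% interval for the risk difference: the Wilson upper limit is 1.96² / (20 + 1.96²) = 16.1% in each arm, so the interval runs from −16.1 to +16.1 points.
- 0 of 60, if all 40 patients of the observational cohort chose ESDT (an assumption at the extreme): 1 − 0.05^(1/60) = 4.9% one-sided.

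**The case against.** The strongest reply is that the harmful step is not in the plan. A reader might infer that the sponsor intends to take a non-significant p-value as proof of safety. No section says so: hypothesis 2 carries no decision rule, Aim 3 speaks of identifying events, and Endpoint 3 is a count. This stands. What remains is that the plan states a safety hypothesis, assigns it a between-group regression, and gives nothing else by which to judge it.

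A reader might also infer that a several-fold excess would usually be missed whatever the event rate. That is not supported. Pain is part of the endpoint and has no definition, so the combined rate could be high. At 60% vs 20% a three-fold excess is missed in only 25-35% of trials, and at 30% vs 5% the likelihood-ratio test misses 38%. The point is about uncommon harms.

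Nor does the document support describing ESDT as left to the patient alone. Study Flow and Recruitment provides for training by a physician and a nurse, care-team direction and weekly calls.

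Logistic regression normally comes with a confidence interval, and counts by arm would allow a bound to be worked out later. Both are true in general, but the row plans neither, and the odds ratio fails when an arm has no events.

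Finally, this is a secondary endpoint in a small trial sized, as is usual, for efficacy. The "at least 80% power" was never promised for harms, so it is no standard to hold them to. That is fair, and it is why the request is for better reporting and not for more patients.

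**Conclusion.** The point holds for uncommon harms. The planned test cannot support hypothesis 2 for events such as perforation: under the assumed risks of 5% vs 1%, 10% vs 2% and 20% vs 5% it misses the excess in 94-100%, 78-99.9% and 63-96% of trials across the two usual logistic tests, and it often has no finite estimate to give. A perforation-free ESDT arm of 20 would leave risks up to about 14% (one-sided) or 17% (two-sided) open.

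The miss rates rest on assumed event risks, a two-sided 0.05 test, 20 analysed per arm and no crossover. Study Flow and Recruitment allows patients in the observation group to move to self-dilation, which would tend to dilute a between-group difference further. The bounds for zero events need no assumed rate.

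The efficacy sample size is not in dispute. Whether anyone would claim safety from a non-significant result cannot be settled from the document; the plan leaves that open, and it can be closed cheaply.

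**What to change.** In the Adverse events row, for perforation, bleeding and pain separately:

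- report the ESDT risk with an exact (Clopper-Pearson) 95% interval;
- report the ESDT-minus-standard-care risk difference with a Newcombe or score 95% interval, which stays finite when an arm has no events;
- keep the logistic regression as descriptive.

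Add two statements: that a non-significant difference in adverse events will not be taken as evidence that ESDT is safe; and that with 20 ESDT patients and no events the trial can exclude only a risk above about 14% (one-sided 95%). Rewording hypothesis 2 as an aim to estimate the risk would fit with this but is optional.

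The cost is a change to one table row and two added sentences, with no new data, visits or patients. The downside for the sponsor is a wide bound in the report in place of an unqualified statement that ESDT is safe.

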This is a prospective randomized controlled trial evaluating the outcomes of self-dilation. Patients who present to the esophageal clinic in Rochester MN and Mayo Clinic Phoenix, AZ with refractory benign esophageal strictures who undergo standard clinical care of serial endoscopic dilation to achieve an esophageal diameter of at least 10-12 mm will be randomized to either continuing standard clinical care consisting of endoscopic dilation as needed vs self-dilation therapy.

Inclusion Criteria for Patients:

- 1. 18 years of age or older
- 2. Refractory benign esophageal stricture defined as an esophageal stricture with persistent dysphagia despite undergoing 5 endoscopic dilations within a 1 year period. Persistent dysphagia will be considered if patients has solid food dysphagia at least once a week

Exclusion Criteria

- 1. Patient with malignant esophageal stricture
- 2. Angulated stricture which prevents safe passage of Maloney dilator in office setting
- 3. In ability to achieve an esophageal diameter of 10 mm with endosocpic dilatiation
- 4. Known significant esophageal motor disorder (i.e. achalasia, aperistalsis, functional obstruction, jackhammer, distal esophageal spasm)*

- 5. The presence of esophageal stent
- 6. Inability to learn self-dilation secondary to blindness or cognitive dysfunction
- 7. Use of chronic anticoagulants

Study Flow and Recruitment

- 1. Patients referred to the esophageal clinic with dysphagia secondary to RBES will be asked to complete the Mayo Dysphagia Questionnaire (MDQ-30). The MDQ will be completed before obtaining informed consent. Quality of life will also be measured at the beginning at end of the 6 months using Short form-36
- 2. First, patients will undergo the standard of care which is serial endoscopic therapy with esophageal dilation. Patients will be dilated 1-3 times a week with the aim to achieve a post-dilation luminal diameter of at least 10-12 mm
- 3. After informed consent, participants will be randomized to one of two groups using a block randomization approach; Group 1) self-dilation, group 2) observation with repeat endoscopy and dilations as needed at symptoms recurrence.
- 4. Patients randomized to self-dilation who refuse self-dilation will be assigned to the observation group and will be counted in the ESDT failure

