- 5. Patients randomized to ESDT will be taught ESDT immediately following the last endoscopic dilation. ESDT teaching will take over 1-3 training sessions by one of two esophageal physicians and a nurse. Patients will be instructed to start ESDT twice a day. If dysphagia is adequately controlled, and there was no resistance with passing the dilator, patients will be asked to decrease the frequency of ESDT to daily, weekly, and monthly over an average period of 6 months as directed by the esophageal care team.
- 6. Patients randomized to the observation group will undergo repeat endoscopy and dilation as needed if their dysphagia relapse which is the current standard of care. A relapse will be considered if a patient developed solid food dysphagia at least once a week.
- 7. Patients in the observation group who requires 2 endoscopic dilation within 3 months will be offered to cross over to the self dilation group
- 8. Patients in the self dilation group who can not tolerate self dilation but require more treatment will be offered to crossover to the standard clinical care grouph endoscopic dilation as needed after 3 months from the entry point
- 9. At the end of the six months, the standard clinical care group will be offered self-dilation.
- 10. At any point of the study if patients decide to crossover to the other group, this will be allowed but counted as treatment failure
- 11. Close supervision and follow up will be performed via weekly phone calls from a member of the study personnellPatients will be asked to complete the MDQ-30 monthly and at the end of the study.
- 12. Patients who decline participation in the randomized study will be offered both treatments clinically then will be followed prospectively and their data will be collected. These patients will be asked to fill the dysphagia score to assess symptoms regardless of the method of treatment.
- 13. At the conclusion of the 6 months randomized or observational study duration patients will be offered the following:
 - 1. All patients who participated in the randomized or observational study will be offered to continue prospective follow up with phone calls to obtain the MDQ-30 score and

need for endoscopy at 3, 6, 9, and 12 months after conclusion of the initial 6 month duration of the study

Remuneration:

- 1. Patients in the randomized self-dilation group will be provided with the self-dilator free of charge.

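### The analysis of factors for ESDT success is an ordinary multivariable logistic model with no stated analysis set; in the sets the plan allows, its odds ratios would often be missing or very imprecise

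*Combined protocol and SAP*

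**What the plan says.** Secondary aim 2 is to "Evaluate factors which could influence clinical success of ESDT including etiology and location of the stricture". In the table at the end of the Statistical Analysis section, the matching row has an approach that opens "Investigating factors which" and then lists age, gender, etiology, stricture length and stricture location as examples, so the list is open. The test is "Multivariate logistic regression". The two other logistic rows in that table name univariate and multivariate analysis; this one names only the multivariate form.

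The documents do not say which patients enter this model. Study Flow and Recruitment creates several groups of possible ESDT users:

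- Patients randomised to ESDT. Those who refuse it "will be assigned to the observation group and will be counted in the ESDT failure" (item 4).
- Controls who need two dilations within three months, who "will be offered to cross over to the self dilation group" (item 7).
- Remaining controls: "At the end of the six months, the standard clinical care group will be offered self-dilation" (item 9).
- Non-randomised patients: "Patients who decline participation in the randomized study will be offered both treatments clinically" (item 12). Sample Size Estimation allows up to 40 of them.

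Under item 10, a patient may change group at any time, and "this will be allowed but counted as treatment failure". The plan does not say whether refusals and crossovers enter the factor model, or whether the 80% success rate already allows for them. It gives no coding for etiology or location, no selection rule and no limit on model terms.

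**The concern.** A logistic model needs enough of the rarer outcome, here ESDT failure, to estimate each slope. With very few failures, some combination of factors often separates failures from successes perfectly or nearly so. The maximum-likelihood odds ratio is then infinite or zero. Software reports non-convergence, or a huge estimate with a huge standard error. When a finite fit does exist, chance alone can produce extreme odds ratios.

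What is at stake is the answer to secondary aim 2. Because the analysis set and coding are open, they could be settled after outcomes are known, and those choices largely decide whether the model can be fitted at all.

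**Working it through.** **Inputs from Sample Size Estimation.** ESDT success 80%, endoscopic dilation success 30%, 1:1 allocation, minimum 30 patients, 40 planned, P value 0.05, at least 80% power.

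**The plan's own figure.** Two-sided test, pooled variance, no continuity correction, mean proportion 0.55:

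n per arm = [1.960 × √(2 × 0.55 × 0.45) + 0.842 × √(0.8 × 0.2 + 0.3 × 0.7)]² / 0.5² = (1.379 + 0.512)² / 0.25 = 14.3, so 15 per arm.

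The stated 30 is reproduced. Approximate power at 20 per arm is 92.1% (84.6% by Fisher's exact test). That calculation concerns only the comparison of arms.

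**Failures available to the factor model.**

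- Randomised ESDT arm: 40 / 2 = 20 patients; 20 × 0.20 = 4 failures; 4 / 5 = 0.8 per slope with one slope per factor. The chance of no failures at all is 0.8²⁰ = 0.012.
- Refusals on top of the 20% (assumed). If 10% refuse and 20% of the rest fail: 0.10 + 0.90 × 0.20 = 28%, or 5.6 failures (1.1 per slope). If 20% refuse: 0.20 + 0.80 × 0.20 = 36%, or 7.2 failures (1.4 per slope).
- Pooled sets (sizes assumed): 40, 60 or 80 users give 8, 12 or 16 failures, that is 1.6, 2.4 or 3.2 per slope. Eighty is the extreme bound: 20 randomised to ESDT, all 20 controls and all 40 observational patients.

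**Does a finite fit exist?** Data sets were simulated with no true association. Age and length were standard normal; gender, etiology and location were binary, split 50/50. These distributions are assumptions, as the documents give none. Separation was detected by linear programming. Joint entry, five slopes:

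| ESDT users | Failure rate | No finite fit |
|---|---|---|
| 20 | 20% | 49% |
| 20 | 28% | 27% |
| 20 | 36% | 15% |
| 40 | 20% | 8% |
| 60 | 20% | 1% |
| 80 | 20% | 0.2% |

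Repeat runs with separate code agree to within about 2 points.

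**Effect of coding.** If etiology or location has three or more equally likely levels (20 patients, 20% failure), the share with no finite fit is 71%, 83%, 94% and 98% for 6, 7, 8 and 9 slopes. With nine slopes it is still 72% at 40 patients and 40% at 60. With only the two factors named in aim 2, each binary, it is 35%, 5%, 0.8% and 0.2% at 20, 40, 60 and 80.

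**Precision when a fit exists** (five slopes, no association, 20% failure):

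| ESDT users | Any of the three binary odds ratios above 5 or below 0.2 | Median ratio of upper to lower 95% limit, binary factor | Any of five Wald p < 0.05 |
|---|---|---|---|
| 20 | 60% | about 430 | 2% |
| 40 | 30% | about 41 | 15% |
| 60 | 14% | about 17 | 21% |
| 80 | 6% | about 11 | 21% |

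Five independent tests at 5% would give 1 − 0.95⁵ = 23%.

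**What penalisation gives.** Firth estimates always exist. For one balanced binary factor at 20% failure, full enumeration gives a type I error of 3% at 20 patients and power for an odds ratio of 5 of 19%, 46%, 62% and 77% at 20, 40, 60 and 80. With no association, the median ratio of upper to lower limit at 20 patients is about 93, and 36% of all data sets still show at least one of three binary odds ratios above 5 or below 0.2.

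**The case against.** The strongest reply is that failure in about half of the fits is one conditional case. It needs the randomised arm alone, a total failure rate of 20%, joint entry and one slope per factor. Of these the documents supply only the 80% success rate; the wording of the row favours joint entry but does not require it. Other admissible choices move the figure from under 1% to 98%. This stands, and the size has to be given as a conditional range.

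It can also be said that the question is minor. It is not among the three hypotheses or the four listed secondary endpoints, and a failed fit is usually visible to the analyst. This limits the weight of the point. It does not remove it: the question is a stated secondary aim, the row is not labelled exploratory, and imprecise finite fits are less visible than failed ones.

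A reader might infer that the randomised arm must be the main set, or that pooling is wrong. The documents do not support that. Age, etiology and location are not randomised, so randomisation does not protect a within-arm analysis of factors, and pooling gains power. Pooling does mix randomised patients with patients selected by preference or by relapse on control, which is a reason for a source term. Likewise, counting refusals as failures mixes willingness with response, and secondary aim 4 already measures acceptance. Either choice is defensible if named beforehand.

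**Conclusion.** The point holds as a conditional statement. Followed as written, the row would often give missing or very unstable odds ratios for secondary aim 2. In the randomised ESDT arm at the plan's own 80% success, no finite fit exists in about half of data sets with five slopes and in about 70% to 98% with six to nine. The five-slope figure is about 15% to 27% if total failures are 28% to 36%, and about 8% down to under 1% in pooled sets of 40 to 80, where imprecision remains, most of all at 40. These sizes rest on joint entry, the assumed factor distributions and levels, the assumed refusal rates and pooled set sizes, and no true association. With moderate association for age, gender and length, the 20-patient five-slope figure was 59%.

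Three stronger readings are not supported:

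- That the primary comparison is compromised. It does not use this model, and the stated sample size reproduces.
- That 20 patients would yield many falsely significant predictors. Only 2% of finite fits show any Wald p < 0.05; the harm is missing or unstable estimates.
- That the same holds for the adverse-events row. The documents give no event rate, so that cannot be worked out.

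**What to change.** In the row on factors for ESDT success, replace the test with:

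*Exploratory. Firth-penalised logistic regression with profile-likelihood 95% intervals, one factor at a time, taking etiology and location (secondary aim 2) first, with their groupings fixed before outcome data are seen. Any jointly adjusted model is also penalised, and its number of terms is limited by the number of failures. No factor is claimed as a predictor on p < 0.05.*

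Name one analysis set in advance and report the alternative as a sensitivity analysis. Two choices are needed: the randomised ESDT arm, or all ESDT users with a term for source; and starters only, or refusals counted as failures. Which set is main is for the sponsor to decide.

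The cost is SAP wording only, with no new patients or data. The downsides are little or no mutual adjustment and low power, about 19% for an odds ratio of 5 at 20 patients. Penalisation guarantees that estimates exist; it does not make them precise, so the results remain descriptive.
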